9.2.5 Procedural Data

- Total procedure time, PVI time, PFA application time, mapping time and PFA application time per lesion
- Total Fluoroscopy Time
- Ablation parameters per application
- Device(s) utilized (per ablation)

9.3 Healthcare Utilization Data

Health care utilization pre-, during and post-hospitalization for the study index ablation procedure, as well as any additional hospitalizations during the study period will be collected. Because this data does not support the safety and efficacy of the VARIPULSE catheter, it will not be provided to the FDA as part of the IDE reporting.

In addition, the sponsor will also collect data associated with follow up care, including any repeat ablation procedure for treating arrhythmia, any inpatient or outpatient visit (including ER admissions, outpatient visits) to address post-procedural complications, any procedure related condition, or any arrhythmia or cardiovascular related conditions.

9.4 Study Timelines

The duration of the study is expected to last approximately 3 years: 6 months for the pilot phase and 2 years for the pivotal phase. The timeline provided below is preliminary and could be revised based on the actual duration of enrollment.

- Pilot Phase:
 - Enrollment will last for approximately 2 months
- Pivotal Phase:
 - Enrollment will last for approximately 12 months.
 - Follow-up duration will be 12 months.

10. Study Population

Patients scheduled to have a clinically indicated ablation procedure for the management of their drug refractory PAF will be screened for enrollment per the study's inclusion and exclusion criteria.

10.1 Subject Selection

The study consists of a PAF population. Subject selection varies is described below.

10.2 Eligibility Criteria

Inclusion Criteria

Candidates for this study must meet ALL of the following criteria:

1. Symptomatic paroxysmal AF with:
 - a. At least two (2) symptomatic AF episodes within last six (6) months from enrollment
 - b. At least one (1) AF episode electrocardiographically documented within 12 months prior to enrollment. Electrocardiographic documentation may include, but is not limited to electrocardiogram (ECG); Transtelephonic monitoring (TTM), Holter monitor or telemetry strip, and
 - c. A physician's note indicating recurrent self-terminating AF within 7 days.
2. Failed at least one (1) AAD (Class I or Class III) as evidenced by recurrent symptomatic AF, intolerable side effects to the AAD, or contraindication to the AAD
3. Age 18-75 years
4. Willing and capable of providing consent
5. Able and willing to comply with all pre-, post- and follow-up testing and requirements.

Exclusion Criteria

Subjects will be excluded from the study if they meet ANY of the following criteria.

1. Previously diagnosed with persistent AF (> 7 days in duration)
2. AF secondary to electrolyte imbalance, thyroid disease, or reversible or non-cardiac cause (e.g., untreated documented obstructive sleep apnea and acute alcohol toxicity).
3. Previous surgical or catheter ablation for AF
4. Patients known to require ablation outside the PV ostia and outside the CTI region (e.g., atrioventricular reentrant tachycardia, atrioventricular nodal reentry tachycardia, atrial tachycardia, ventricular tachycardia and Wolff-Parkinson White)
5. Documented severe dilatation of the LA (LAD >50mm) antero-posterior diameter on imaging within 6 months prior to enrollment.
6. Documented LA thrombus by imaging within 48 hours of the procedure.

7. Documented severely compromised LVEF (LVEF <40%) by imaging within 6 months prior to enrollment
8. Uncontrolled heart failure or New York Heart Association (NYHA) Class III or IV
9. History of blood clotting, bleeding abnormalities or contraindication to anticoagulation (heparin, warfarin, or dabigatran),
10. Documented thromboembolic event (including TIA) within the past 12 months
11. Previous PCI/MI within the past 2 months
12. Coronary Artery Bypass Grafting (CABG) surgery within the past 6 months (180 days)
13. Valvular cardiac surgical/percutaneous procedure (i.e., ventriculotomy, atriotomy, valve repair or replacement and presence of a prosthetic valve).
14. Unstable angina within 6 months
15. Anticipated cardiac transplantation, cardiac surgery, or other major surgery within the next 12 months.
16. Significant pulmonary disease (e.g., restrictive pulmonary disease, constrictive or chronic obstructive pulmonary disease) or any other disease or malfunction of the lungs or respiratory system that produces severe chronic symptoms.
17. Significant congenital anomaly or medical problem that in the opinion of the investigator would preclude enrollment in this study
18. Prior diagnosis of pulmonary vein stenosis
19. Pre-existing hemi diaphragmatic paralysis
20. Acute illness, active systemic infection, or sepsis
21. Presence of intracardiac thrombus, myxoma, tumor, interatrial baffle or patch or other abnormality that precludes catheter introduction or manipulation.
22. Severe mitral regurgitation (Regurgitant volume \geq 60 mL/beat, Regurgitant fraction \geq 50%, and/or Effective regurgitant orifice area \geq 0.40cm²)
23. Presence of implanted pacemaker or Implantable Cardioverter-Defibrillator (ICD) or other implanted metal cardiac device that may interfere with the IRE energy field.
24. Presence of a condition that precludes vascular access (such as IVC filter)
25. Current enrollment in an investigational study evaluating another device or drug.
26. Women who are pregnant (as evidenced by pregnancy test if pre-menopausal), lactating, or who are of child-bearing age and plan on becoming pregnant during the course of the clinical investigation.
27. Life expectancy less than 12 months
28. Presenting contra-indications for the devices used in the study, as indicated in the respective Instructions for Use (IFU).

10.3 Subject Enrollment and Retention

Study sites will be selected for participation in the study based on experience with single shot (RF or Cryo) catheter technology, ablation experience, their capacity to screen and enroll a reasonable number of eligible patients, and ability to perform the required procedures, according to this protocol.

Historically, women and minorities have been underrepresented in or excluded from many clinical studies, leading to a lack of information for women and their physicians regarding the risk and benefits

of many medical treatments and diagnostic procedures. It is the Sponsor's intent to apply the principles from FDA's guidance titled Evaluation of Sex-Specific Data in Medical Device Clinical Studies in this clinical trial to ensure adequate representation of women and minorities. The Sponsor will take reasonable steps to ensure adequate representation of women and racial or ethnic minorities in this clinical trial including:

In order to reflect the gender ratio of the intended population, Sponsor plans to enroll approximately 70% males and 30% females in the study. The gender ratio (male: female = 7:3) undergoing ablation procedures in the AF population is estimated based on previous studies. ^[39]

Sites will be instructed to screen all subjects who may be eligible for participation in the study without regard to sex or race. Statistical analysis of primary safety and effectiveness endpoints will be carried out to evaluate any interaction between treatment and gender. Subjects will be encouraged to remain in the study until they have completed the protocol required follow-up period.

Sponsor will attempt to include a diversified group of research sites engaging a variety of academic and private institutions geographically located throughout the US. To ensure generalizability of results and minimize the influence of any single site, no more than 15% of the total enrollment will be allowed at a single site for both study populations.

10.4 Subject Withdrawal/Early Termination

Subjects may withdraw from the clinical investigation at any time. The decision for the subject to withdraw informed consent must be made independently of influence by the investigator or site personnel. The subject's decision will be documented in the source and eCRF. The investigator may also choose to withdraw a subject from the study if there are safety concerns. If a subject withdraws from the study, the date for withdrawal will be recorded on the appropriate electronic case report form (eCRF).

All data will be collected (as available) until the subject is withdrawn. If the subject is withdrawn due to an adverse event (AE) or serious adverse event (SAE), the investigator should follow the subject until the AE/SAE has resolved or is considered stable.

Subjects who have signed the ICF but are found to be ineligible PRIOR to insertion of the study catheter will be recorded as screen failures in the eCRF.

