10.5 Subjects Lost to Follow-Up

Subjects should be encouraged to return for protocol required, clinic visits for evaluation during the study follow-up period. If a subject is unable to return for an office or clinic visit or unable to be contacted by telephone, 3 separate telephone calls should be made to obtain subject related safety information. All attempts should be documented in the source documents. If the subject does not respond to the 3 telephone calls, then the investigator must send a certified letter to the subject. If the subject does not respond to the letter within 4 weeks, then the subject will be considered "lost to follow-up" for the study.

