10.6 Subject Disposition

- **Enrolled Subjects:** subjects who sign the study ICF.
- **Excluded Subjects:** subjects who are enrolled but never undergo insertion of the study catheter. Excluded subjects will not be included in the primary endpoint analyses and will only be followed between the time of ICF signature and exclusion from the study for adverse event reporting. Subjects who signed the ICF but are found to be ineligible prior to the procedure will be recorded as screen failures in the eCRFs.
- **Evaluable Subjects:** all enrolled subjects who have the study catheter inserted.
- **Discontinued Subjects:** evaluable subjects who have the study catheter inserted but do not undergo ablation (i.e., no PFA energy is delivered with the study catheter). Discontinued subjects will remain in follow-up for 3 months post catheter insertion. If a SAE is reported for a discontinued subject, the subject will be followed until event resolution (with or without sequelae), stabilization, or until the event is adequately explained.
- **Lost to Follow-up Subjects:** subjects who are evaluable, but contact is lost after most recent follow-up visit (despite 3 documented attempts to contact the subject).
- **Withdrawn / Early Termination Subjects:** subjects who withdraw consent for study participation or are withdrawn/terminated from the study by the investigator prior to completion of all follow-up visits.
- **Completed Subjects:** enrolled subjects who have not been excluded, discontinued, withdrawn, terminated early, or lost-to-follow-up prior to the final study visit and have completed the 12-month follow up visit.

11. Responsibilities

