- Complete all subject follow-up visits, including efforts to maintain contact with subjects who fail to comply with the follow-up schedule. Before a subject may be classified as 'lost to follow-up', the Investigator or authorized personnel should document 3 attempts to contact the subject.
- Retaining study records as described in Section 20.2. The Sponsor will notify the Investigator when records may be destroyed.
- Preparing a final report and periodic IRB updates as required.

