8.5 Analysis of Primary Endpoint(s)

8.5.1 Analysis of Primary Safety Endpoint

In the Pilot phase and the Pivotal roll-in phase, the primary safety endpoint will be summarized descriptively using the total number of PAEs, the number of subjects who experience PAEs, and the percentage of subjects who experience PAEs. The SA will be used to analyze the PAE data from the Pilot phase, while the Roll-In analysis set will be used to analyze the safety data from the Pivotal roll-in phase.

In the Pivotal main phase, hypothesis testing will be performed in the mITT analysis set. Subjects with non-missing PAE outcome data will be included in the primary analysis. The primary safety endpoint will be evaluated using the exact test for a binomial proportion at a one-sided significance level of 2.5%. If the upper bound of the exact two-sided 95% confidence interval of the primary safety endpoint rate is less than the performance goal of 12%, the study will be considered to have demonstrated safety.

To investigate the robustness of the analysis result, sensitivity analyses including estimation of the PAE rate in the SA, worst-case and best-case scenario analyses, and tipping point analysis will be performed in the SA and mITT analysis sets. Details are provided in Section 8.6.

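### Investigator withdrawal under Protocol 10.4 stops routine outcome collection in treated subjects, and Protocol 10.6 defines loss to follow-up more loosely than 10.5, so obtainable primary outcomes can go missing

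*Protocol*

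**What the plan says.** **Withdrawal.** Protocol 10.4 allows subjects to leave at any time and adds: "The investigator may also choose to withdraw a subject from the study if there are safety concerns". On data it says "All data will be collected (as available) until the subject is withdrawn". There is one exception: when an AE or SAE is the reason for withdrawal, "the investigator should follow the subject until the AE/SAE has resolved or is considered stable". Protocol 10.6 places subjects who withdraw consent and subjects withdrawn by the investigator in a single disposition class. Neither section separates stopping visits from refusing further data collection.

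**Loss to follow-up.** Three sections speak to this:
- Protocol 10.5 asks for three telephone calls. It then says "If the subject does not respond to the 3 telephone calls, then the investigator must send a certified letter to the subject", and the status applies "If the subject does not respond to the letter within 4 weeks".
- Protocol 10.6 defines the class as evaluable subjects where "contact is lost after most recent follow-up visit (despite 3 documented attempts to contact the subject", with no letter and no waiting time.
- Protocol 11.1 says that, before the status is assigned, "the Investigator or authorized personnel should document 3 attempts to contact the subject". It mentions neither the letter nor the wait.

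**Analysis.** For safety, SAP 8.5.1 states: "Subjects with non-missing PAE outcome data will be included in the primary analysis". SAP 8.5.2 applies the same restriction to effectiveness. Best-case, worst-case and tipping-point analyses are planned for both primary endpoints, with Kaplan-Meier estimation added for effectiveness. Their details, the missing-data rules in SAP 8.10 and the analysis-set definitions are redacted.

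**The concern.** The study treatment is an ablation procedure, sometimes followed by a repeat. Once a subject has been treated, leaving the study mainly ends observation. What stops is the scheduled ECG, transtelephonic and Holter monitoring, and the recording of repeat ablation, cardioversion and Class I/III drug use. All of these feed the primary effectiveness endpoint.

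For safety, most primary adverse events have a 7-day window and would usually be known before any withdrawal. The exposed components are tamponade or perforation (30 days), atrio-esophageal fistula (90 days), pulmonary vein stenosis (12 months), device- or procedure-related death (any time) and permanent phrenic nerve paralysis, which is judged at final follow-up.

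Subjects withdrawn because of a safety concern, or who stop answering, are unlikely to be a random sample of those treated. Leaving them out of a single-arm comparison with a fixed performance goal could move the estimate in the favorable direction. The two loss-to-follow-up rules add to this, because a site working from 10.6 could close a subject whom the letter required by 10.5 might have recovered.

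**Working it through.** **Inputs.** SAP section 1: 248 enrolled, from 225 evaluable plus 10% attrition. SAP 8.4.1, 8.5.1 and 8.5.2: performance goals of 12% (safety) and 50% (effectiveness), judged by exact two-sided 95% limits. The assumed true rates are redacted.

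**The plan's own figure.** 225 × 1.10 = 247.5, rounded up to 248, so the allowance is 248 − 225 = 23 subjects. (Dividing by 0.90 would give 250; the difference is immaterial here.) Protocol 10.6 counts anyone with the study catheter inserted as evaluable, including those lost later. Read literally, the 225 may therefore already contain subjects with no 12-month outcome.

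**Limits.** For s successes in n, the exact lower limit is the 0.025 quantile of Beta(s, n − s + 1). For x subjects with an event, the exact upper limit is the 0.975 quantile of Beta(x + 1, n − x).

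**Effectiveness.** Take 225 observed outcomes with s successes, then add k subjects who failed unseen. The table gives the smallest k for which the lower limit of s/(225 + k) is at or below 50%.

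| Successes of 225 | Rate | Lower limit as analyzed | Smallest k | Lower limit with k added |
|---|---|---|---|---|
| 128 (fewest that pass) | 56.9% | 50.14% | 1 | 49.90% |
| 130 | 57.8% | 51.03% | 5 | 49.85% |
| 132 | 58.7% | 51.93% | 9 | 49.80% |
| 135 | 60.0% | 53.28% | 14 | 49.94% |
| 140 | 62.2% | 55.54% | 24 | 49.82% |

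At 140 successes, k already exceeds the full allowance of 23.

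**Safety.** 17/225 is the largest count that passes (upper limit 11.82%). One unseen event gives 18/226 (12.30%) and two give 19/227 (12.76%); both fail. Starting from 10/225, nine unseen events are needed.

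**Power compared with bias.** Suppose 22 of 225 have no outcome. The test on the remaining 203 needs 116 successes (57.1%). At an assumed true rate of 60%, power falls only from 84.6% to 81.7%. If all 22 had failed, however, 116/225 = 51.6%, which is 128 − 116 = 12 successes short of a pass. The exposure is therefore bias.

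**How many subjects.** The documents give no number. If 1% to 3% of 225 are affected (an assumption), that is about 2 to 7 subjects. With every one of them a failure, the result would change only for observed counts of 128 to 131.

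**The case against.** A reader might infer that withdrawal ends all data collection. It does not. Protocol 10.4 keeps AE/SAE follow-up going after a withdrawal that the event caused, 14.8 requires follow-up information until resolution or stabilization, and 14.2.1 has reported primary adverse events monitored until resolved or explained. Many safety-driven withdrawals fall under these clauses. They follow a known event, though. They do not require rhythm monitoring, and they do not look for a later, different event.

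A reader might also infer that two sections permit closure after three attempts. Only 10.6 does. Protocol 11.1 states a precondition, which is compatible with 10.5; its weakness is that it omits the letter and the wait.

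Nor can it be said that withdrawal prevents no exposure. Enrollment begins at consent, so 10.4 also covers subjects not yet treated. Under 13.4, repeat procedures for recurrence in the blanking period use the study catheter for reconnected veins, so withdrawal could avert a second use.

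Finally, the numerical examples sit near the decision boundary. Failures before withdrawal are collected, the sponsor tracks missing data (20.1.4) and may seek further medical documentation (20.2.1), and sensitivity analyses are planned. All of this stands and limits the size of the point. But the sensitivity analyses can only bound what is missing; they cannot supply an outcome that a call or a record check would have given.

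**Conclusion.** The point holds as a worthwhile, low-cost improvement. Followed as written, 10.4 stops routine collection of effectiveness outcomes and later extended-window safety outcomes in treated subjects whom the investigator withdraws. Protocol 10.5 and 10.6 disagree on when a subject is lost, and SAP 8.2 builds the disposition summary on 10.6, the looser of the two. Both primary tests then exclude subjects with missing outcomes.

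The consequence is possible bias, and it could decide the trial only in a close result: up to about 60% observed success if as many as 14 unseen failures are conceivable, and no longer at 62.2% even if the whole 23-subject allowance failed. For safety, it could decide the result if the count is at or just below 17 of 225. This rests on two things the documents do not give: how many subjects would be affected, and how their outcomes differ from the rest. A reader might conclude that primary outcomes will certainly be lost. The documents show only that they can be. No fault is found in the redacted missing-data rules. The consent pages are not available, so it cannot be judged whether consent already allows record checks after withdrawal.

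**What to change.** **In Protocol 10.4 and 10.6**, for subjects who have had the study catheter inserted, distinguish:
- (a) stopping study visits or tests, whether by the subject's or the investigator's decision; and
- (b) withdrawing consent to data collection.

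For (a), the site continues by phone or from records to Day 365 to collect AEs, vital status, repeat ablation, cardioversion, Class I/III antiarrhythmic use and any available ECG. This is subject to consent and to the existing 3-month follow-up for Discontinued subjects. Only (b) ends collection. Report the two as separate disposition classes.

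**In Protocol 10.6**, replace the three-attempt wording with a reference to Section 10.5, and add the same reference in 11.1. State that follow-up resumes if a subject reappears before Day 365.

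**Cost.** A protocol wording amendment, possibly one sentence in the consent form, and phone or record checks for what should be a small number of subjects. The subject's right to withdraw is untouched, and neither the sample size nor the primary tests change.

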10.5 Subjects Lost to Follow-Up

Subjects should be encouraged to return for protocol required, clinic visits for evaluation during the study follow-up period. If a subject is unable to return for an office or clinic visit or unable to be contacted by telephone, 3 separate telephone calls should be made to obtain subject related safety information. All attempts should be documented in the source documents. If the subject does not respond to the 3 telephone calls, then the investigator must send a certified letter to the subject. If the subject does not respond to the letter within 4 weeks, then the subject will be considered "lost to follow-up" for the study.

10.6 Subject Disposition

- **Enrolled Subjects:** subjects who sign the study ICF.
- **Excluded Subjects:** subjects who are enrolled but never undergo insertion of the study catheter. Excluded subjects will not be included in the primary endpoint analyses and will only be followed between the time of ICF signature and exclusion from the study for adverse event reporting. Subjects who signed the ICF but are found to be ineligible prior to the procedure will be recorded as screen failures in the eCRFs.
- **Evaluable Subjects:** all enrolled subjects who have the study catheter inserted.
- **Discontinued Subjects:** evaluable subjects who have the study catheter inserted but do not undergo ablation (i.e., no PFA energy is delivered with the study catheter). Discontinued subjects will remain in follow-up for 3 months post catheter insertion. If a SAE is reported for a discontinued subject, the subject will be followed until event resolution (with or without sequelae), stabilization, or until the event is adequately explained.
- **Lost to Follow-up Subjects:** subjects who are evaluable, but contact is lost after most recent follow-up visit (despite 3 documented attempts to contact the subject).
- **Withdrawn / Early Termination Subjects:** subjects who withdraw consent for study participation or are withdrawn/terminated from the study by the investigator prior to completion of all follow-up visits.
- **Completed Subjects:** enrolled subjects who have not been excluded, discontinued, withdrawn, terminated early, or lost-to-follow-up prior to the final study visit and have completed the 12-month follow up visit.

11. Responsibilities

